7 STATISTICS AND METHODS OF DATA ANALYSIS

7.1 SAMPLE SIZE RATIONALE

The sample size is based on experience from the VTI-208 study.

Analysis of the VTI-208 data suggests that in a group of subjects meeting the inclusion criteria for VTL-308 it might be reasonably anticipated that the hazard rate in the control group will be 0.004 and the hazard ratio 0.4 in favor of the ELAD group. Under the assumption of a proportional hazards model, this leads to median survival estimates of approximately 175 days and 438 days for Control and ELAD subjects, respectively.

The VTL-308 inclusion criteria have been established to reflect the same study population as that enrolled in a subset of the VTI-208 population with baseline criteria including MELD <30, age <50, INR \leq 2.5, creatinine <1.3 and serum total bilirubin \geq 16mg/dL, to define the ITT population, with key safety criteria also applied prior to initiation of ELAD treatment and at End of Study Day 2 (EOSD 2) in the Control group to establish the mITT population. Applying these criteria to the analysis of the primary endpoint of overall survival in the ITT population, and assuming: 1) that this prospectively-defined population behaves similarly to this subgroup of the VTI-208 study; 2) the use of a log-rank test comparing two survival curves with a two-sided significance level of 0.05; 3) exponential survival curves with proportional hazards; 4) uniform accrual with an accrual time of at least 720 days and a minimum follow-up time of 90 days; and 5) a drop-out rate of 10%, a sample size for VTL-308 of 75 subjects per group with 1:1 allocation is consistent with power of at least 0.95 with estimated median survival times of 175 and 438 days respectively.

Due to the distribution of subjects between the ITT and mITT group it may be necessary to enroll more than 150 subjects total in order to ensure that there are a minimum of 75 subjects actually treated with ELAD in the ITT population. Consequently, enrollment may continue until ELAD treatment has been initiated on 75 subjects.

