9.1 ADVERSE EVENTS

The safety of all subjects enrolled in this study will be monitored throughout the study. Safety monitoring will include history and physical examination with vital signs, adverse event reporting, and laboratory evaluations. Adverse events will be collected and recorded for subjects from Randomization through Study Day 91, or until subject discontinuation within this 91-day period.

ELAD is a combination biologic and medical device product that is regulated as a medicinal product in the US and EU where the study is being conducted. However, adverse events need to be assessed and reported following both the drug and medical device regional requirements.

The Investigator is responsible for assessment of all AEs/SAEs for severity and relationship to the assigned treatment. All SAEs must be reported by the Investigator to the VTL Designee within 24 hours of knowledge. The VTL Designee will report SAEs that meet the criteria for expedited reporting (per the [Investigator's Brochure](#)) to the appropriate health authorities in accord with regional requirements. The Investigator must submit these expedited reports to their IRB/EC in accord with local requirements. Further detail is provided below.

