1.3 SAMPLE SIZE RATIONALE

The sample size is based on experience from the VTI-208 study.

The VTL-308 inclusion criteria have been established to reflect a subset of the VTI-208 population, i.e. the VTI-208 population with baseline criteria of MELD <30, age <50, INR \leq 2.5, creatinine <1.3 mg/dL and serum total bilirubin \geq 16 mg/dL.

The key design feature of the VTL-308 Protocol is that the primary analysis of treatment effect on overall survival is based on a log-rank statistic having two-sided significance level of 0.05. This primary analysis will be performed when the last of 150 randomized subjects has been followed for at least 91 days. Sample size adjustments may be made only in the instance in which more than 150 randomized subjects would be needed in order to achieve the minimum threshold of 55 deaths at the time of that analysis.

When the study is nearing completion of enrollment, the total number of deaths occurring through that time will be calculated, along with the mortality rate, based on the enrollment rate per month and the time to death. Based on these calculations a projection will be made of the total number of subjects that will need to be enrolled to achieve the minimum threshold of 55 deaths at the time of study data lock (estimated to be approximately 5 months after last patient enrolled). The total sample size may then be adjusted accordingly.

Analysis of the VTI-208 data suggests that in a group of subjects meeting the inclusion criteria for VTL-308, it might be reasonably anticipated that one-year survival will be in the range from 40% to 48% in the Control group. Under the assumption of a proportional hazards model, if the hazard ratio is 0.4 in favor of the ELAD group, this leads to the anticipation that one-year survival will be in the range from 69.5% to 74.5% in the ELAD subjects.

The rationale for the sample size is based on the following assumptions:

- the analysis of the primary endpoint of overall survival will be conducted in the ITT population;
- the prospectively defined population behaves similarly to the corresponding subgroup of the VTI-208 study;
- the log-rank test will be used to compare two survival curves using a two-sided significance level of 0.05;
- one-year survival will be in the range from 40% to 48% in the Control group and in the range from 69.5% to 74.5% in the ELAD group;
- the accrual distribution will be uniform with an accrual time that will be at least 720 days;

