7.3.7 Outcome relative to Infection, Fluid Overload/Fluid Loss and Bleeding

Proportion of survivor tables at Study Day 28 and at Study Day 91 will be presented by treatment group and by infection. Ongoing infection at Randomization, infection which emerged as a TESAE between Randomization and Day 7, between Day 8 and Day 14 and between Day 15 and Day 28, will be summarized separately. Proportion of survivors at Study Day 91 will be summarized by treatment group by subjects who developed an infection TESAE between Day 29 and Day 91. Differences between treatment groups within each infection group will be analyzed based on a Chi-squared test. Additionally, differences between infection group, regardless of treatment, will be analyzed based on a Chi-square test.

Proportion of survivor tables at Study Day 28 and at Study Day 91 will be presented by treatment group and by occurrence of fluid overload or loss events. Fluid overload or loss events which emerged as a TESAE between Randomization and Day 7, between Day 8 and Day 14, and between Day 15 and Day 28, will be summarized separately. Proportion of survivors at Study Day 91 will be summarized by treatment group by subjects who developed a fluid overload or loss event TESAE between Day 29 and Day 91. Differences between treatment groups within each fluid overload or loss group will be analyzed based on a Chi-squared test. Additionally, differences between fluid overload or loss group, regardless of treatment, will be analyzed based on a Chi-square test.

Proportion of survivor tables at Study Day 28 and at Study Day 91 will be presented by treatment group and by occurrence of bleeding. Bleeding which emerged as a TESAE between Randomization and Day 7, between Day 8 and Day 14, and between Day 15 and Day 28, will be summarized separately. Proportion of survivors at Study Day 91 will be summarized by treatment group by subjects who developed a bleeding TESAE between Day 29 and Day 91. Differences between treatment groups within each bleeding group will be analyzed based on a Chi-squared test. Additionally, differences between bleeding group, regardless of treatment, will be analyzed based on a Chi-square test.

Subjects that die, are lost to follow up or withdraw from the study during one of these periods will not be included in the summaries covering subsequent periods for the above analyses.

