8.3 ADVERSE EVENTS

The number and percent of subjects with treatment-emergent adverse events (TEAEs), TEAEs leading to ELAD discontinuation, TEAEs leading to ELAD treatment interruptions, TEAEs classified by their highest relationship to study drug, and TEAEs classified by their maximum severity, will be summarized by treatment group and by MedDRA System Organ Class and Preferred Term. Individual listings of all TESAEs, all deaths, and all TEAEs leading to ELAD discontinuation/interruption will be prepared.

Treatment-emergent adverse events are defined as those AEs with an onset date/time on or after the randomization date/time. The rationale for this is that subjects in both treatment groups are receiving standard of care at the time of Randomization. In addition summary tables of TEAEs and TESAEs will be presented based on treatment and post-treatment study periods. The study periods used in analysis for ELAD-treated subjects will be defined as Pre-ELAD (Randomization date/time to ELAD start date/time), ELAD Treatment (ELAD start date/time to Study Day 7), D8-D14 (Study Day 8 to Study Day 14) and D15-D91 (Study Day 15 to Study Day 91); and for Control subjects, Rand-D2 (Randomization date/time to Study Day 2), D3-D7 (Study Day 3 to Study Day 7), D8-D14 (Study Day 8 to Study Day 14) and D15-D91 (Study Day 15 to Study Day 91). Additional summaries of TEAEs that started between Randomization and ELAD treatment start, and TEAEs/TESAEs that started after ELAD treatment start will be presented by MedDRA System Organ Class and Preferred Term for subjects in the ELAD treatment group. For comparison purposes within these summary tables, TEAEs that started between Randomization and Study Day 2, and TEAEs/TESAEs that started after Study Day 2 will be presented for subjects in the Control treatment group.

Treatment-emergent adverse events will be coded using Medical Dictionary for Regulatory Activities (MedDRA) (Version 18.1) and incidences will be compared between treatment groups using MedDRA Preferred Terms within System Organ Classes. Subjects will only be counted once within each level of summarization.

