8.3.1.1.2 Infections post-randomization

A listing of all TESAEs of infection post-randomization by subject using the terms included in **Appendix B** will be generated. The TESAEs of infection will include the following parameters: treatment group, subject ID, AE ID, SOC/Investigator term/MEDRA Preferred Term, start date/time, and stop date/time; outcome; relationship to any of the ELAD components (VTL C3A cells, System, and Procedure); whether concomitant medications (Yes/No) were administered to treat the infection; whether steroids were administered (Yes/No) to treat the alcoholic hepatitis based on a start date between Post-randomization up to Study Day 28 (to assess risk for infection); and any action taken with ELAD (i.e., prompted discontinuation). This listing will be sorted into two sections; one section will list those subjects who have an ongoing infection at randomization and the other section will list those subjects who do not have an ongoing infection at randomization.

The total number of TESAEs of infection emerging post-randomization will be summarized by Preferred Term and treatment group.

The number of subjects with at least one TESA of infection post-randomization, the number of subjects that also had an ongoing infection at baseline or no ongoing infection at baseline, and the number of subjects with at least one TESA of infection that also had a positive blood culture that occurred during the same time period as the infection, will also be summarized in separate tables for the periods between Randomization and Study Day 7, between Study Day 8 and Study Day 14, between Study Day 15 and Study Day 28 and between Study Day 29 and Study Day 91.

8.3.1.2 *Fluid Overload/Fluid Loss*

All TESAEs of fluid overload and fluid loss that emerged following randomization up to Study Day 91 for each subject will be identified by the terms listed in [Appendix C](#).

The total number of TESAEs of fluid overload/fluid loss emerging post-randomization will be summarized by Preferred Term and treatment group.

The number of subjects with at least one TESAЕ of fluid overload/fluid loss post-randomization, will also be summarized in separate tables for the periods between Randomization and Study Day 7, between Study Day 8 and Study Day 14, between Study Day 15 and Study Day 28 and between Study Day 29 and Study Day 91.

8.3.1.3 *Bleeding*

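### SAP 8.3 compares adverse-event percentages between arms with no allowance for time at risk, so late-period percentages partly reflect survival; separately, the first two periods differ in length by arm.

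*SAP*

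**What the plan says.** SAP 8.3 tabulates the number and percentage of subjects with treatment-emergent adverse events (TEAEs). It adds TEAE and serious-event (TESAE) tables by study period and closes with the general statement that "incidences will be compared between treatment groups using MedDRA Preferred Terms within System Organ Classes". SAP 6.2 names Fisher's exact or chi-squared tests for categorical safety variables. SAP 8 makes the Safety population the default set. No denominator is given for the period tables, and no rate per unit of follow-up is planned.

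SAP 7.3.7 tabulates survival by infection, fluid and bleeding events over successive periods. There, subjects who die, are lost or withdraw "will not be included in the summaries covering subsequent periods for the above analyses". SAP 8.3.1 uses the same event types and windows, including "between Study Day 15 and Study Day 28 and between Study Day 29 and Study Day 91", without that rule. It asks for numbers of subjects and events, not percentages.

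For ELAD-treated subjects, the first two periods in SAP 8.3 are "Pre-ELAD (Randomization date/time to ELAD start date/time), ELAD Treatment (ELAD start date/time to Study Day 7". For Control they run to Study Day 2 and then from Study Day 3 to 7. The later periods (Days 8-14 and 15-91) are the same in both arms.

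Protocol 9.1 limits collection: "Adverse events will be collected and recorded for subjects from Randomization through Study Day 91, or until subject discontinuation within this 91-day period".

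**The concern.** A subject who has died cannot contribute a later adverse event. Where mortality is high and the planned survival difference is large, the arm with more deaths has less time in which events can be seen. A crude percentage then mixes event risk with survival. If ELAD prolongs life, late non-fatal events look more frequent on ELAD at equal rates. If ELAD raised early mortality, the same feature would hide late harm.

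The early periods raise a different problem. They contain the extracorporeal exposure itself, yet one arm's window moves with the treatment start and the other's is fixed. Percentages over windows of unequal length are not comparable.

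**Working it through.** **Inputs.** Protocol 7.1: "hazard rate in the control group will be 0.004 and the hazard ratio 0.4 in favor of the ELAD group", so h = 0.004 per day for Control and 0.4 × 0.004 = 0.0016 for ELAD. SAP 1.3: "one-year survival will be in the range from 40% to 48% in the Control group", with the same hazard ratio.

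**Reproducing the plan's figures.** The protocol says "this leads to median survival estimates of approximately 175 days and 438 days for Control and ELAD subjects, respectively". With median = ln 2 / h, the results are 173 and 433 days, about 1% off. For the SAP, h = -ln(0.40)/365 = 0.00251 and -ln(0.48)/365 = 0.00201. ELAD one-year survival is 0.40^0.4 = 69.3% and 0.48^0.4 = 74.6%, against the stated 69.5% and 74.5%. The two documents differ in substance: h = 0.004 implies one-year Control survival of exp(-1.46) = 23%. SAP 1.1 gives the SAP precedence in an analysis conflict, so its range leads here.

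**Time at risk.** With exponential survival, expected days at risk per subject from day a to day b are [exp(-ha) - exp(-hb)]/h. Days 15-91 use a = 14 and b = 91. With equal constant event rates and all subjects in the denominator, the ELAD/Control ratio of these days is the apparent excess in events:

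| Window | SAP, 48% | SAP, 40% | Protocol, h = 0.004 |
|---|---|---|---|
| Days 0-7 | 1.004 | 1.005 | 1.008 |
| Days 8-14 | 1.013 | 1.016 | 1.025 |
| Days 15-91 | 1.064 | 1.081 | 1.131 |
| Days 0-91 | 1.055 | 1.069 | 1.110 |

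For Days 15-91, the days at risk are 69.35 against 73.83, 67.60 against 73.06, and 62.66 against 70.84 (Control against ELAD).

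**Counting each subject once.** Incidence at event rate r is exp(-ha) × r/(r+h) × [1 - exp(-(r+h)(b-a))]. This lowers the excess slightly. At the protocol hazard, for Days 15-91, it is 12.7% for an event with a 20% risk over the window and 11.9% for one with a 50% risk.

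**Denominator of subjects alive at period start.** Dividing each arm's days at risk by exp(-ha) gives a Days 15-91 ratio of 1.093 at the protocol hazard and 1.047 to 1.058 under the SAP. Most of the excess remains, because deaths within the window still shorten follow-up. Events per subject-day give 1.00 under these assumptions.

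**Serious events including fatal ones.** Protocol 9.4 requires the cause of each death to be reported as a serious event. Adding one such event per death, the incidence of any TESAE is exp(-ha) × [1 - exp(-(r+h)(b-a))]. For Days 15-91 at the protocol hazards:
- r = 0.005 per day (assumed): Control 0.9455 × (1 - exp(-0.693)) = 47.3%; ELAD 0.9778 × (1 - exp(-0.508)) = 39.0%.
- r = 0.02 per day (assumed): 79.7% and 79.3%.

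The excess on ELAD disappears or reverses.

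**Early windows.** The footnotes to Protocol Table 3 foresee ELAD starts beyond End of Study Day 3. A start exactly then leaves 4 × 24 = 96 hours to the end of Study Day 7, against 5 × 24 = 120 for Control (ratio 0.80), and a pre-treatment window 24 hours longer than Control's. If Control's two windows are taken as 2 and 5 days, a start at day 1 gives ratios of time at risk of 0.50 before treatment and 1.21 on treatment. A start at day 3 gives 1.50 and 0.81.

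**The case against.** The percentage of subjects with an event is a legitimate measure of absolute risk, and no efficacy claim or stopping rule in the plan rests on these tables. That stands, and it is a reason to keep the percentages beside a rate. The plan also partly handles the early windows. SAP 8 explains that End of Study Day 2 was chosen to approximate ELAD start, SAP 8.3 adds summaries of everything after ELAD start against everything after Study Day 2, and SAP 8.2 reports the mean time to ELAD start. The documents give no distribution of start times, so the 96-hour case is only an illustration.

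Four stronger readings are tempting, and the documents do not support them:
- **That the SAP keeps dead subjects in the period denominators.** It does not say so. This is the default reading of a Safety-population table with no denominator stated.
- **That adverse events in general will look 11-15% higher on ELAD.** This needs the protocol hazard and the long windows. The 15% belongs to Days 29-91, which appears only in SAP 8.3.1, where counts are specified.
- **That the unequal early windows add to an excess on ELAD.** A late start shortens the ELAD treatment window and lowers its apparent incidence; an early start does the reverse.
- **That the better ELAD works, the worse its late safety profile looks.** This fails for summaries of any serious event, as the calculation shows. It holds only for non-fatal events.

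**Conclusion.** The concern holds in a limited form. SAP 8.3 compares crude percentages without regard to time at risk, and nothing elsewhere in SAP 8 corrects this. For non-fatal events with equal true rates, Days 15-91 incidence would look about 6-8% higher on ELAD under the SAP's survival range and about 13% higher under the protocol's hazards. The shared early windows are little affected (about 1% or less to Day 7, and at most 2.5% for Days 8-14). These figures assume exponential survival, a hazard ratio of 0.4, a constant event rate unrelated to death, and no loss to follow-up. They change with Control mortality and vanish if survival does not differ.

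The unequal first two periods are a separate defect of uncertain direction. The primary efficacy analysis is untouched, but the safety comparison should be corrected before the tables are programmed.

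**What to change.** In SAP 8.3 and the period tables of 8.3.1:
- Keep the percentages or counts and state the denominator for each period.
- Add events, or subjects with a first event, per 100 subject-days at risk. Time runs from period start to the earliest of period end, death, withdrawal or Day 91, and also stops at the first event where subjects are counted once.
- Base the between-arm comparison on that rate. This also accounts for the differing lengths of the first two periods.
- Show fatal and non-fatal serious events separately.

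Extending the 7.3.7 rule to these tables would settle the denominator, but it would leave about 9% in Days 15-91 at the protocol hazard and compare survivors selected after randomization. The rate column is the part that works.

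The cost is SAP wording and extra columns, using dates already collected. The rate assumes a roughly constant hazard within each period, which is least secure over Days 15-91.

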8.3.1 Adverse Events of Special Interest

8.3.1.1 Infections

8.3.1.1.1 Infections prior to Randomization

Infections that occur prior to Randomization are listed in the Liver Medical History or the General Medical History, and will be identified by the terms listed in **Appendix B**. Each of these infections has an onset date and a stop date. If the stop date is prior to the date of Randomization, the infection will be considered resolved at Randomization, and if the stop date is after Randomization the infection will be considered ongoing at Randomization. In order for a subject to be eligible for the study all infections ongoing at time of Randomization had to be controlled.

A listing of infections occurring prior to Randomization will be generated. It will be split into two sections. The first will include all infections resolved by Randomization, i.e. those with a stop date prior to Randomization. The second will include all infections listed as ongoing at Randomization (i.e. those with a start date prior to randomization and a stop date after randomization).

The number of subjects with at least one ongoing infection at Randomization will be summarized by treatment group, and the number of subjects with one ongoing infection, two ongoing infections and three or more ongoing infections at Randomization will be summarized by treatment group and Preferred Term.

8.3.1.1.2 Infections post-randomization

A listing of all TESAEs of infection post-randomization by subject using the terms included in **Appendix B** will be generated. The TESAEs of infection will include the following parameters: treatment group, subject ID, AE ID, SOC/Investigator term/MEDRA Preferred Term, start date/time, and stop date/time; outcome; relationship to any of the ELAD components (VTL C3A cells, System, and Procedure); whether concomitant medications (Yes/No) were administered to treat the infection; whether steroids were administered (Yes/No) to treat the alcoholic hepatitis based on a start date between Post-randomization up to Study Day 28 (to assess risk for infection); and any action taken with ELAD (i.e., prompted discontinuation). This listing will be sorted into two sections; one section will list those subjects who have an ongoing infection at randomization and the other section will list those subjects who do not have an ongoing infection at randomization.

The total number of TESAEs of infection emerging post-randomization will be summarized by Preferred Term and treatment group.

The number of subjects with at least one TESA of infection post-randomization, the number of subjects that also had an ongoing infection at baseline or no ongoing infection at baseline, and the number of subjects with at least one TESA of infection that also had a positive blood culture that occurred during the same time period as the infection, will also be summarized in separate tables for the periods between Randomization and Study Day 7, between Study Day 8 and Study Day 14, between Study Day 15 and Study Day 28 and between Study Day 29 and Study Day 91.

8.3.1.2 *Fluid Overload/Fluid Loss*

All TESAEs of fluid overload and fluid loss that emerged following randomization up to Study Day 91 for each subject will be identified by the terms listed in [Appendix C](#).

The total number of TESAEs of fluid overload/fluid loss emerging post-randomization will be summarized by Preferred Term and treatment group.

The number of subjects with at least one TESAЕ of fluid overload/fluid loss post-randomization, will also be summarized in separate tables for the periods between Randomization and Study Day 7, between Study Day 8 and Study Day 14, between Study Day 15 and Study Day 28 and between Study Day 29 and Study Day 91.

8.3.1.3 *Bleeding*

All TEAEs and TESAEs of bleeding that emerged following randomization up to Study Day 91 for each subject will be identified by the terms listed in [Appendix D](#).

Two series of separate tables will be generated for the periods between Randomization and Study Day 7, between Study Day 8 and Study Day 14, between Study Day 15 and Study Day 28 and between Study Day 29 and Study Day 91. The first series will summarize the total number of TEAEs of bleeding emerging post-randomization by Preferred Term and treatment group, and the number of subjects with at least one bleeding TEAE, with more than one bleeding TEAE, along with the number of subjects administered heparin for ELAD treatment or for DVT prophylaxis. The second series will summarize the total number of TESAEs of bleeding emerging post-randomization by Preferred Term and treatment group, and the number of subjects with at least one bleeding TESAЕ, with more than one bleeding TESAЕ, along with the number of subjects administered heparin for ELAD treatment or for DVT prophylaxis.

In addition the number of subjects reporting at least one TEAE and also the number of subjects reporting at least one TESAЕ will be summarized by Preferred Term and treatment group.

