Abdominal distension	Device related sepsis	Hypernatraemia	Multi-organ failure
Acute respiratory distress syndrome	Disseminated intravascular coagulation	Hypersensitivity	Oedema peripheral
Agitation	Ecchymosis	Hypertension	Oliguria
Allergic reaction	Edema	Hypocalcemia	Pain
Anaemia	Edema peripheral	Hypocoagulable state	Pneumonia
Anuria	Electrolyte imbalance	Hypofibrinogemaemia	Pulmonary oedema
Application site bleeding	Encephalopathy	Hypokalaemia	Renal failure acute
Ascites	Epistaxis	Hypomagnesaemia	Respiratory arrest
Asthma	Fever	Hypophosphataemia	Tachycardia
Atrial fibrillation	Fluid overload	Hypotension	Thrombocytopenia
Bacteremia	Gastrointestinal haemorrhage	Hyothermia	Vessel puncture site haematoma
Blood lactate dehydrogenase (LDH) increased	Gingival bleeding	Hypovolemia	Wound secretion
Blood pressure decreased	Haematemesis	Ileus	
Catheter site hematoma	Haematuria	Infection	
Catheter site hemorrhage	Hemoglobin decreased	Injection site haemorrhage	
Catheter site pain	Hemolysis	Ischemic hepatitis	
Catheter site reaction	Haemorrhage	Leukocytosis	
Coagulation disorder	Hepatic encephalopathy	Melaena	
Coagulation prolonged	Hepatic failure	Mental status changes	

¹ Listed alphabetically

Expected Adverse Events: Extracorporeal Procedures

Certain adverse events are typically observed in patients undergoing treatment with extracorporeal procedures. Anemia, coagulopathy, and thrombocytopenia tend to be the most common adverse events observed during treatment with extracorporeal procedures. Specific details about each of these adverse events are presented in the following sections.

Anemia

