Appendix C Fluid Overload/Fluid Loss Symptoms Search Terms

Ascites

Oesophageal varices haemorrhage

Upper gastrointestinal haemorrhage

Generalised oedema

Oedema peripheral

Edema without specification

Acute respiratory distress syndrome

Acute respiratory failure

Hypoxia

Pleural effusion

Pulmonary oedema

Respiratory arrest

Respiratory failure

Renal failure (any type)

Hypotension (any type)

Shock (any type)

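### The SAP's search list for fluid overload and fluid loss has no direct term for either condition, and the subject-level and survival tables do not separate the two directions

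*SAP*

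**What the plan says.** SAP 8.3.1.2 makes fluid overload/fluid loss one of three groups of adverse events of special interest, beside infections and bleeding. Its identification rule is that "All TESAEs of fluid overload and fluid loss that emerged following randomization up to Study Day 91 for each subject will be identified by" the Appendix C list, which is titled "Fluid Overload/Fluid Loss Symptoms Search Terms". The SAP gives no other route into the set.

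Three outputs use the set:

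- **Event counts (8.3.1.2).** "The total number of TESAEs of fluid overload/fluid loss emerging post-randomization will be summarized by Preferred Term and treatment group".
- **Subject counts (8.3.1.2).** "The number of subjects with at least one TESAЕ of fluid overload/fluid loss post-randomization, will also be summarized in separate tables", for four periods up to Study Day 91. Overload and loss are not split.
- **Survival at Study Days 28 and 91 (7.3.7).** Tables are given by treatment group and "by occurrence of fluid overload or loss events", with chi-squared tests between arms within each fluid-event group and between the groups regardless of treatment.

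The expected-event table in Protocol Appendix D lists "Fluid overload" and also *Hypovolemia*. Protocol Section 9 tells sites to enter the syndrome or diagnosis on the eCRF and not each associated sign or symptom.

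SAP 8.3 separately tabulates all treatment-emergent events by System Organ Class, Preferred Term and arm, and lists every serious one.

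**The concern.** The rule promises to find all serious events of two named conditions, using a list of their manifestations and consequences that omits the conditions themselves. The recording instruction in Protocol Section 9 makes this more than a formality. A site that follows it and enters the diagnosis may produce exactly the record that a symptom list does not retrieve.

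The second problem is direction. "Pulmonary oedema" and "Upper gastrointestinal haemorrhage" sit in the same list and count towards the same subject-level category, together with respiratory and renal failure terms that point to neither direction. The special-interest set should give a grouped answer per subject on whether ELAD is associated with overload or with loss. As specified, the grouped count may be incomplete and mixes the two. In 7.3.7 a survival difference between subjects with and without a fluid event could reflect haemorrhage, shock or respiratory failure and say little about fluid balance.

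**Working it through.** The documents state no rate for these events, so there is no figure to reproduce. The first three steps are a text check. The last three are an illustration on assumed rates.

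**1. Content of the list.** The Appendix C entries are ascites (1), gastrointestinal haemorrhage terms (2), generalised, peripheral and unspecified oedema (3), pulmonary oedema (1), pleural effusion (1), respiratory failure, arrest, ARDS and hypoxia terms (5), renal failure (1), hypotension (1) and shock (1). The total is 1+2+3+1+1+5+1+1+1 = 16. Entries matching *Fluid overload*: 0 of 16. Entries matching *Hypovolemia*: 0 of 16. There is no hypervolaemia or dehydration term either.

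**2. Comparison with the protocol.** Protocol Appendix D lists both missing terms as expected events, so the sponsor anticipates that sites may report them.

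**3. Trace of one case.** A subject has a serious event coded only *Fluid overload*, and no Appendix C event in the same period.

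| Output | Is the event seen? |
|---|---|
| SAP 8.3 tables by Preferred Term | Yes |
| SAP 8.3 listing of serious events | Yes |
| SAP 8.3.1.2 event count | No |
| SAP 8.3.1.2 subject count | No |
| SAP 7.3.7 survival tables | Subject classed as having no fluid event |

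The last row assumes that 7.3.7 uses the Appendix C set. Section 7.3.7 does not cite the appendix, but the SAP defines the events nowhere else.

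**4. Dilution by pooling.** Assumptions: 75 subjects per arm (SAP 1.3), overload 20% on ELAD and 5% on Control, and other listed events at an arm-equal rate x, independent of overload. The pooled rate is 1 − (1 − overload)(1 − x), so the arm difference is (0.20 − 0.05)(1 − x).

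Power serves only as a yardstick, at two-sided 0.05: Φ[(d − 1.96·SE0)/SE1], with SE0 = √(2p̄(1−p̄)/75) and SE1 = √([pE(1−pE) + pC(1−pC)]/75). For overload alone, p̄ = 0.125, SE0 = 0.0540 and SE1 = 0.0526, so the power is Φ[(0.15 − 0.1059)/0.0526] = Φ(0.84) = 0.799.

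| x | ELAD | Control | Difference (points) | Power |
|---|---|---|---|---|
| 0 (overload alone) | 20.0% | 5.0% | 15.0 | 0.799 |
| 10% | 28.0% | 14.5% | 13.5 | 0.525 |
| 30% | 44.0% | 33.5% | 10.5 | 0.260 |
| 50% | 60.0% | 52.5% | 7.5 | 0.150 |

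**5. Incomplete capture.** If the list misses 25%, 50% or 75% of overload cases equally in both arms, the captured rates are 15% vs 3.75%, 10% vs 2.5% and 5% vs 1.25%. Power is 0.660, 0.475 and 0.260.

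**6. When pooling would cancel.** An at-least-one-event count adds events and does not net them. With overload at 20% vs 5%, the pooled difference reaches zero if loss is 5% vs 20%: 1 − 0.80×0.95 = 24% and 1 − 0.95×0.80 = 24%. If loss is also 20% vs 5%, the pooled rates are 1 − 0.80² = 36% and 1 − 0.95² = 9.75%. The difference then grows to 26.25 points.

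**The case against.** The strongest reply is that no event is lost to the report. SAP 8.3 tabulates every treatment-emergent event by Preferred Term and arm, adds tables by study period, and lists every serious event. Within the special-interest set, captured events are also shown by Preferred Term and arm. This stands. A reader might infer that the ELAD fluid risk would be missed altogether, or that the SAP cannot show it at all. The documents do not support either reading.

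A reader might also infer that pooling cancels an ELAD effect. That needs opposite arm effects of similar size, and Protocol Appendix D suggests no such pattern. It lists haemorrhage and hypotension as expected ELAD System events, and bleeding and hypotension as general risks of plasma filtration. If loss is also more frequent on ELAD, pooling enlarges the difference.

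Further points stand in part:

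- Some episodes coded as pulmonary oedema, oedema, hypotension or shock would be captured. How many is unknown.
- The expected-event table is not shown to be a list of coded Preferred Terms, and MedDRA 18.1 itself is not in the documents. The exact terms to add must be taken from the dictionary.
- The heading of that table is not in the available text. Attributing *Fluid overload* to a particular ELAD component would be inference.
- The SAP assigns no direction to any entry, so sorting them is a clinical judgement.
- Some entries also fall under the infection or bleeding lists (SAP Appendices B and D). A reader might take this for double counting, but no planned analysis adds the three sets together.
- The fluid tables are descriptive, and 7.3.7 is exploratory. No primary or secondary endpoint depends on them.

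None of this removes the core. The rule says it finds all serious events of two conditions and contains no direct term for either. Unlike the bleeding section (8.3.1.3), the fluid section gives no subject counts by Preferred Term to offset the pooling.

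**Conclusion.** The point holds as a defect in an identification rule and in how one special-interest set is tabulated. Direct terms for the two named conditions: none among 16 entries. Events coded only with such terms drop out of the 8.3.1.2 counts, and their subjects can be placed in the wrong group in 7.3.7. They remain visible in the general tables and listing. Pooling dilutes or obscures direction.

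The size in this trial cannot be known from the documents. Under the assumed 20% vs 5% overload rates with 75 per arm, an arm-equal rate of other listed events between 10% and 50% lowers the visible difference from 15.0 to between 13.5 and 7.5 points. Missing half the overload cases lowers power from 0.799 to 0.475. These figures rest on assumed rates, on independence between event types and on equal capture in both arms. The text finding does not depend on them. The primary survival analysis is unaffected.

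**What to change.** Before database lock:

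1. Add to SAP Appendix C the MedDRA 18.1 Preferred Terms that directly name fluid overload/hypervolaemia and hypovolaemia.
2. Have the medical monitor assign the existing entries to an overload list or a loss list, and record the assignment in the appendix. Entries that fit neither stay in the pooled set only.
3. Produce the 8.3.1.2 subject-level period tables and the 7.3.7 survival tables separately for overload and for loss. Keep the pooled table as an addition.
4. State in 7.3.7 that its fluid events are those defined by Appendix C.

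The cost is an appendix edit and one extra set of descriptive tables, whose cells will be smaller than in the pooled version. No new data are needed.
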